### 12.5 Study Documentation

# 12.5.1 Informed Consent and Authorization for use and Disclosure of Protected Health Information

Written informed consent and authorization of use and disclosure of protected health information (PHI) must be obtained from each subject (or the subject's legally authorized representative) before performing any study-specific screening/baseline period evaluations. One copy of the signed informed consent form (ICF) and authorization for use and disclosure of the PHI form will be given to the subject and the investigator will retain the original. The ICF and authorization for use and disclosure of PHI, which is prepared by the investigator or the site, must be reviewed and approved by the Protocol Chair, the study monitor (if applicable) and the site's IRB before the initiation of the study. The ICF must contain the 20 elements of informed consent described in ICH E6, Section 4.8. The authorization for use and disclosure of PHI must contain the elements required by Title 45 of the Code of Federal Regulations (CFR), Section 164.508(b), for valid authorizations.

## 12.5.2 Investigator Study Files

Documentation about the investigator and study staff, the IRB and the institution, is required before study site initiation. A list of required documents will be provided by the Protocol Chair or designee to each participating investigator. Copies of these documents as well as supplemental information, such as the investigator's obligations, IB, clinical study protocol and amendments, safety information, investigational agent information, biological samples and laboratory procedures, SRM, study logs and Protocol Chair/investigator/study monitor correspondence will be kept on-site in study site-specific files.

The Protocol Chair or designee will be responsible for maintaining original and backup of all CRF data. The investigator is responsible for maintaining backup of all electronic data systems used for primary documentation or source documentation. Backup of electronic data will be performed periodically as described in the site-specific SOPs. Backup records must be stored at a secure location on site and backup and recovery logs must be maintained to facilitate data recovery. If an electronic

medical records system that is not supported by the Protocol Chair or designee (or is discontinued or decommissioned) is used, the investigator must maintain a system to retrieve these records or arrange for the transfer of these records to an alternate electronic format or to paper.

Changes to any electronic records require an audit trail, in accordance with 21 CFR 11.10(e), and should include who made the changes and when and why the changes were made. An audit trail is defined as a secure, computer-generated, time-stamped electronic record that will allow reconstruction of the course of events relating to the creation, modification and deletion of an electronic record. Audit trails must be created incrementally, in chronological order and in a manner that does not allow new audit trail information to overwrite existing data. Audit trails should be in a readable format and readily available at the study site and any other location where electronic study records are maintained.

Audit trails are generated automatically for eCRFs. The investigator is responsible for maintaining audit trails of all electronic data systems used for primary documentation or source documentation.

# 12.5.3 Case Report Forms and Source Documentation

The investigator must make study data accessible to the site monitor, to other authorized representatives of the Protocol Chair (or designee) and to the appropriate regulatory authority inspectors. The original CRF for each subject will be checked against source documents at the study site by the site monitor.

### 12.5.4 Retention of Study Documents

According to ICH E6, Section 4.9, all CRFs, as well as supporting paper and electronic documentation and administrative records, must be retained for at least 2 years after the last approval of a marketing application and until there are no pending or contemplated marketing applications, or at least 2 years have elapsed since the formal discontinuation of clinical development of an individual product. Longer retention periods may apply. The Protocol Chair will notify investigators as to when documents no longer need to be retained. No study documents will be destroyed or moved to a new location without prior written approval from the Protocol Chair. If the investigator relocates, retires or withdraws from the clinical study for any reason, all records required to be maintained for the study should be transferred to an agreed-upon designee, such as another investigator at the institution where the study was conducted.

Audit trails for electronic documents must be retained for a period at least as long as that required for the subject electronic records to which they pertain. The investigator must retain either the original or a certified copy of audit trails.

## 12.5.5 Data Confidentiality and Subject Anonymity

All information about the nature of the proposed investigation provided by the Protocol Chair or their representative to the investigator (with the exception of information required by law or regulations to be disclosed to the IRB, the subject or the appropriate regulatory authority) must be kept in confidence by the investigator.

The anonymity of participating subjects must be maintained. Subjects will be identified by their initials and an assigned subject number on CRFs and other documents retrieved from the site or sent to the Protocol Chair, AstraZeneca, McGuff, regulatory agencies, or central laboratories/reviewers. Documents that identify the subject (e.g., the signed ICF) must be maintained in strict confidence by the investigator, except to the extent necessary to allow auditing by the appropriate regulatory authority, the study monitor, Protocol Chair or their representative.

#### 13.0 STATISTICAL CONSIDERATIONS

# 13.1 Study Design

This pilot trial has an exact single-stage design. It will evaluate olaparib and IV ascorbate in patients with metastatic castration resistant prostate cancer in which a DNA repair mutation is absent. The hypothesis of the study is that olaparib will synergize with IV ascorbic acid to improve clinical outcomes in this population.

**Primary objective:** To estimate the proportion of patients with metastatic castration resistant prostate cancer (mCRPC) having a 50% reduction in PSA from baseline (PSA50 response).

#### Secondary objectives:

- 1) To evaluate the safety and tolerability of olaparib in combination with IV ascorbic acid in patients with mCRPC.
- 2) To estimate the median radiographic progression free survival (rPFS) of patients with mCRPC receiving olaparib in combination with IV ascorbic acid
- 3) To estimate the median time to PSA doubling from baseline of patients with mCRPC receiving olaparib in combination with IV ascorbic acid.
- 4) To estimate the median PSA progression free survival (PSA PFS) of patients with mCRPC receiving olaparib in combination with IV. ascorbic acid
- 5) To assess overall survival (OS) in patients with castration resistant prostate cancer.

**Exploratory objectives:** Examine correlates that may be predictive of the clinical outcomes: PSA50 response and rPFS

- 1) To quantify ctDNA and perform mutational analysis in the peripheral blood and compare it to any baseline germline or somatic mutations (document prestudy on case report form)
- 2) To quantify circulating tumor cells (CTCs) in the peripheral blood at baseline, 4 weeks, 12 weeks, and upon progression and assess γH2AX foci in CTCs
- 3) Optional γH2AX foci FFPE biopsy tissues
- 4) To measure F2-isoprostanes in the urine as a pharmacodynamic measure of oxidant injury at baseline, 4 weeks, 12 weeks, and upon progression.
- 5) To measure 8-oxo-2'-deoxyguanosine as a measure of oxidative stress in the urine at baseline, 4 weeks, 12 weeks, and upon progression.

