# 13.2 Primary Endpoint Definition

The primary endpoint in this study is based on  $PSA_{50}$  response.  $PSA_{50}$  response will be defined as a decrease in the PSA to 50% less than the baseline PSA upon enrollment in the trial. The decrease must be confirmed by a second measurement at least 4 weeks apart. PSA values will be measured monthly during the trial.

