# 13.5 Sample Size/Accrual Rate

Accrual to this study is expected to be one patient per month. For this combination to be considered for further study a  $PSA_{50}$  response of 23% or more would be desirable. Our null hypothesis of 3% is based on the low  $PSA_{50}$  response rate, 3% (1 of 33), reported by Mateo et al. for this patient population. This single-stage design has a 95% chance ( $\alpha$  = 0.05) of rejecting the therapy if the true percentage of patients with some benefit from treatment is less than or equal to 3% and an 80% chance of concluding the therapy is beneficial if the true percentage is 23% or more. Twelve patients, will be assessed for 6 months and if 2 or more achieve a  $PSA_{50}$  response, the therapy will be considered for a larger study. Patients enrolled who never receive any study related therapy will be

replaced. Enrollment would be allowed to continue, up to a maximum of 15 patients, to replace those patients that drop-out early.

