# 13.9 Exploratory/Correlative Analysis

The additional correlative analyses will be primarily descriptive in nature. Plots (e.g. histograms, scatter and spaghetti plots) and summary statistics (medians, ranges, counts, proportions) will be used to summarize patterns over time and compare outcomes. Comparisons in the pre- and post-treatment responses will be compared using paired ttests (or Wilcoxon signed rank tests if appropriate) for continuous variables and McNemar's tests for dichotomous or categorical variables. Peripheral blood samples will be analyzed for ctDNA, CTCs and  $\gamma$ H2AX foci in CTCs at serial time points during the study in order to identify therapeutic targets, biomarkers, and predictors of response. Additionally, urine samples will be analyzed for F2-isoprostane and 8-oxo-2'-deoxyguanosine levels at serial time points during the study in order to identify the impact of study therapy on oxidative toxicities, which will be correlated to therapeutic outcomes.

Genomic sequencing library construction, whole genome/exome sequencing, whole transcriptome sequencing, microbial sequencing, neoepitope prediction, mutation burden, and bioinformatic analysis will be performed either at an on-campus laboratory or at an off-campus sequencing service. All the samples will be de-identified before sending to any laboratory for sequencing. The FASTQ files, BAM files and VCF files will be generated and analyzed. Genomic sequencing data will be stored and computations conducted using a JH IT managed subscription of Azure.

Results from the sequencing studies will not be released to the patients. These studies are for research purposes only and are not using a clinically validated platform

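### PSA50 yes/no is the only PSA outcome named for the biomarker analyses; with 12 men it will rarely show a predictor, and the monthly PSA already collected would carry more information as a continuous outcome

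*Combined protocol and SAP*

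**What the plan says.** Sections 2.3 and 13.1 set the aim of the correlative work. In Section 13.1 it is to "Examine correlates that may be predictive of the clinical outcomes: PSA 50 response and rPFS". The markers are ctDNA, CTCs with γH2AX foci, and urinary F2-isoprostanes and 8-oxo-2'-deoxyguanosine. Section 13.9 says the blood samples will be analysed "at serial time points during the study in order to identify therapeutic targets, biomarkers, and predictors of response".

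On the PSA data, Section 13.2 says "PSA values will be measured monthly during the trial", and the study calendar (Section 7.1) places the draw on Day 1 of each 28-day cycle. No continuous PSA outcome (percent change, log change or slope) is defined anywhere.

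On numbers, Section 13.5 says "Twelve patients, will be assessed for 6 months and if 2 or more achieve a" PSA50 response, the combination goes forward. Enrolment may run "up to a maximum of 15 patients, to replace those patients that drop-out early".

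Section 13.9 calls the correlative analyses mainly descriptive. It names tests for pre- against post-treatment comparisons but none for marker against outcome. Sections 13.4 and 13.9 also speak more loosely of therapeutic outcomes, and Section 11.2.2 of patient response.

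**The concern.** PSA50 is a cut of a continuous measurement. For the primary endpoint the cut has a good reason: the historical comparator, 1 of 33, exists only on that scale. The biomarker analyses have no such comparator, so nothing in the plan requires the cut there.

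Its price depends on the number of responders. If only none, one or two of 12 men respond, a responder/non-responder comparison says almost nothing about any marker, while the PSA courses of all 12 men remain available.

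Two statements in the plan raise the stakes. Section 13.6 gives the value of the correlative data as one reason for having no futility monitoring. Section 11.2.1 expects to be able to predict in retrospect which patients respond. If the combination proves inactive, the marker data should still be readable, and on the PSA50 scale they would mostly not be.

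**Working it through.** **Inputs.** All are from Section 13.5: 12 patients and a cut of 2 or more responders; a 3% null rate ("Our null hypothesis of 3% is based on the low" historical rate, 1 of 33); and "an 80% chance of concluding the therapy is beneficial if the true percentage is 23% or more". The correlation between marker and PSA change is not given for a baseline marker, so it is assumed and varied.

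**1. The plan's own design.** With X ~ Binomial(12, p), P(X = k) = C(12,k) p^k (1−p)^(12−k).
- At 3%: P(0) = 0.97^12 = 0.694 and P(1) = 12 × 0.03 × 0.97^11 = 0.258, so P(X ≤ 1) = 0.951. The attained one-sided alpha is 0.0486.
- At 23%: P(0) = 0.77^12 = 0.043 and P(1) = 12 × 0.23 × 0.77^11 = 0.156, so P(X ≤ 1) = 0.199. Power is 0.801.

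The stated 0.05 and 80% are reproduced.

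**2. Responders available to the marker analyses.** The expected count is 12 × 0.03 = 0.36 or 12 × 0.23 = 2.76. These are means, not limits: at 23%, P(X ≥ 4) = 1 − 0.710 = 0.29.

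**3. What a responder split can show.** With k responders of 12 and no ties, the smallest two-sided exact rank-sum p-value is 2/C(12,k):

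| k | Smallest p |
|---|---|
| 0 | no comparison |
| 1 | 2/12 = 0.167 |
| 2 | 2/66 = 0.030 |
| 3 | 2/220 = 0.009 |

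A 5% result is impossible for k ≤ 1. That event is the same as missing the go rule, so its probability comes from step 1: 95% at a 3% rate and 20% at 23%. With k = 2, only perfect separation suffices.

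**4. Comparison of the two scales.** Marker and log PSA change were simulated as bivariate normal with correlation rho. A responder is a patient whose PSA change is beyond the quantile that matches the response rate. The PSA50 split was tested by exact rank-sum, with no rejection counted when nobody responds; continuous PSA change was tested by Spearman correlation. Power for n = 12, one marker, two-sided 5%:

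| Assumed rho | Continuous PSA | PSA50 split, 23% rate | PSA50 split, 3% rate |
|---|---|---|---|
| 0.34 | about 16% | 8% | under 1% |
| 0.5 | 34% | 15% | 1% |
| 0.6 | 48% | 22% | 1% |
| 0.8 | 85% | 43% | 3% |

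Repeated runs agree to within about two points. The value 0.34 corresponds to a Spearman correlation of about 0.33, the only marker-to-PSA correlation in the documents. Section 11.2.1 cites it for on-treatment ctDNA change against PSA change, so it does not fix the size for a baseline marker.

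**5. If all 15 men are analysed.** P(X ≤ 1) is 93% at 3% and 11% at 23%. At rho 0.6, power is 61% on the continuous scale, against 32% (23% rate) or 3% (3% rate) for the split.

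**The case against.** The strongest reply is that these analyses are labelled descriptive, claim no power, and specify no rank-sum test of a marker by PSA50 status. That stands: no stated figure is wrong, and the power values above only measure how much information each scale holds. It does not remove the point, because a descriptive responder/non-responder display also fails with no responders or one, whereas a scatter plot against PSA change does not.

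A second reply is that continuous PSA is not excluded. The looser wording in Sections 11.2.2, 13.4 and 13.9 and the planned scatter and spaghetti plots leave room for it, and rPFS is a second named outcome. This also stands: the continuous outcome is unspecified, not forbidden. Naming it in advance would limit later choice among best change, 12-week change and slope.

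A third reply is that 12 patients limit the study at least as much as the cut does. At rho 0.34 this is right. The gain is then about 8 points, and the continuous scale would still miss a real marker about five times in six.

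The simulation is also idealised. It gives each man one PSA change and models neither the confirmation required for PSA50 nor early stopping.

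A reader might infer that a real predictor cannot be found on the PSA50 scale, or that failure is certain if the therapy is inactive. The figures do not support this. Impossibility holds only with no responders or one, which has a 95% chance at 3% and a 20% chance at 23%. A reader might also infer that the reason given in Section 13.6 collapses. It does not: the correlative data include paired pre/post changes and ctDNA mutation patterns, which do not depend on the responder count.

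**Conclusion.** The point holds as an inexpensive improvement to exploratory analyses. With PSA50 as the only named PSA outcome and 12 men, a real predictor of PSA response is very unlikely to be seen at the 3% rate (power 3% or less throughout) and hard to see at 23% (8% to 43% over correlations of 0.34 to 0.8). The continuous scale gives about 16% to 85% over the same range, whatever the response rate.

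This rests on assumed correlations, the bivariate normal model, one marker at a time and no adjustment for multiple markers or time points. At modest correlations both scales remain low-powered. The primary endpoint, its 2-of-12 rule and the stated design figures are unaffected.

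**What to change.** Leave PSA50 and the 2-of-12 rule as they are for the primary endpoint. In Sections 2.3, 13.1, 13.4 and 13.9:

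- Name the log ratio of PSA to baseline at C4D1 (week 12) as the PSA outcome for the correlative analyses. If a patient stops earlier, use the last on-treatment value and mark that point on the plots.
- Report a Spearman correlation with a 90% confidence interval and a scatter plot, both for baseline markers and for on-treatment marker changes.
- Keep the PSA50 split as a descriptive display, and keep rPFS as the second outcome.

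The cost is plan wording and one derived variable from values already collected, with no new visits, samples or patients. The downside is that men who stop early contribute PSA at an earlier time, which may be related to why they stopped; marking those points makes this visible but does not remove it.

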# 13.2 Primary Endpoint Definition

The primary endpoint in this study is based on  $PSA_{50}$  response.  $PSA_{50}$  response will be defined as a decrease in the PSA to 50% less than the baseline PSA upon enrollment in the trial. The decrease must be confirmed by a second measurement at least 4 weeks apart. PSA values will be measured monthly during the trial.

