# 7.1 Study Calendar

Required Studies	Pre-study 	1 cycle = 28 days		EOT 	LONG TERM FU 			
	Screening	C1D1 	C1D8	C1D15 	C1D22 	CnDn 		
Visit Windows (days) 	-28	+/-3	+/-3	+/- 3	+/-3	+/- 3	-28	+/-28
TREATMENT								
Olaparib		X	X	X	X	X		
Ascorbic acid 		X	X	X	X	X		
ELIGIBILITY								
Inclusion/exclusion review	X							
HRR status 	X							
Informed consent	X							
ECG	X							
PHYSICAL								
Medical and Cancer History	X							
Physical Exam, Weight and ECOG 	X	X	X	X	X	X	X	X
Vital Signs 	X	X	X	X	X	X	X	X
AE/Toxicity Notation 		X	X	X	X	X	X	X
Concurrent meds 	X	X	X	X	X	X	X	X
LABORATORY								
Chemistry 	X	X	X	X	X	$X^7$	X	X
Hematology 	X	X				$X^7$	X	X
Urinalysis	X							
INR and PT/APTT 	X							
Urine Creatinine 	X 	X 				X 	X 	
Testosterone	X							
PSA 	X	X				$X^7$	X	X
G6PD 	X							
CORRELATIVE								
Blood Samples 	NA	X 				X 	$X^{10}$	
Urine Samples 	NA	$X^{11}$				$X^{11}$	$X^{11}$	
Optional Biopsy (Encouraged)	X 	N/A				X 		
DISEASE ASSESSMENT								
Radiologic Evaluation/ RECIST 1.1  or PCWG2	X 					X 	X 	
LONG TERM FOLLOW-UP 								X 

- Longer delays to be approved by the study sponsor. IRB approval is required for all eligibility waivers prior to enrollment. The window for the baseline Radiologic Evaluation/RECIST 1.1 is 6 weeks prior to C1D1.
- Each treatment cycle is 4 weeks (28 days). Ascorbic Acid dosing must be 2 times per week except week 1 when Olaparib is giving alone. The first infusion must occur on day 1 of each cycle and the second infusion can occur any other day during the week as long as it is at least 24 hours from the prior infusion.
- Ports are recommended but not mandatory due to the frequency of infusion.
- 4 After screening, physical exams may be limited as indicated by symptoms. ECOG Eastern Cooperative Oncology Group performance status. Physical exam (including vital signs and weight), ECOG status, AE/Toxicity notation and concurrent medication review have a -3 day window of day 1 of the cycle.

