- Vital signs will be collected prior to infusion. Vital signs include temperature, blood pressure, respiration rate, and heart rate. Height is collected prestudy only. There is a -3 day window of day 1 of each cycle that the vital signs can be collected within.
- 6 Clinical Hematology: CBC with differential ANC, ALC, AEC, and platelet count; Serum Chemistry: sodium, potassium, chloride, bicarbonate, glucose, BUN, creatinine, ALT, AST, alkaline phosphatase, total bilirubin, total protein, albumin, calcium.
- Safety labs and PSA may be collected within a window of up to 3 days prior to scheduled visit/dosing. As of Cycle 2 and further cycles: at Day 1 visit, hematology and chemistry should be collected per hold parameters; at Days 8, 15, and 22 visits, only chemistry will be collected per hold parameters (hematology does not need to be drawn on Days 8, 15, and 22 unless clinically indicated). After C1D1, PSA is collected at CnD1 only (i.e., not weekly).
- 8 Urine creatinine will be collected at C1D1, C2D1 (4 weeks), C4D1 (12 weeks), and at EOT.
- G6PD testing: Red blood cell hemolysis may occur in people found to be deficient in the G6PD enzyme.
- Up to 50mL of whole blood will be collected for ctDNA analysis at each time point. Blood samples should be drawn at screening (or pre-dose C1D1), C2D1 post infusion (4 weeks), C4D1 (12 weeks) post infusion, and at EOT. Bloods do not need to be collected at C1D1 if they were collected within 7 days prior to the visit. γ H2AX will also be assessed at C1D1, C1D8, C2D1, C4D1 and progression.
- Urine samples of up to 15mL will be collected to assess F2-isoprostanes and 8-oxo-2'-deoxyguanosine at screening (or pre-dose C1D1), C2D1 (4 weeks), C4D1 (12 weeks), and at EOT. Urine samples do not need to be collected at C1D1 if they were collected within 5 days prior.
- 12 Research samples will be collected at the discretion of the PI based on availability of supplies and safety of patient and staff. An optional biopsy at baseline and at C4D1 (+/- 2 weeks) will be performed to look for γH2AX in tissue.
- CT scan (chest/abdomen/pelvis or MRI if patient has contrast allergy) and bone scan to be assessed at baseline and every 12 weeks (+/- 1 week), and at EOT (if clinically indicated by PI/Sub-I).

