# 7.3 Treatment/Intervention Period

Patients will be seen on D1 of each cycle of study therapy (consisting of 28 days  $\pm$ 3 days). The following assessments will be performed at each visit:

- Conduct physical exam (including vital signs, weight)
- Obtain and medical history changes from prior assessment
- Assess performance status (ECOG). (Appendix A)
- Review concurrent medications

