## 13.7 Analysis of Primary Endpoint

The primary endpoint is based on  $PSA_{50}$  response. All patients who receive at least one dose of olaparib and IV ascorbic acid will be evaluable for the primary objective. If patients do not have adequate PSA data after the initiation of therapy due to stopping for toxicity or withdrawing consent, then they will be considered unevaluable. The  $PSA_{50}$  response will be calculated as a proportion with 90% confidence intervals.

**PSA**50 **response** will be defined as a decrease in the PSA to 50% less than the baseline PSA upon enrollment in the trial. Patients must receive at least one dose of olaparib and IV ascorbic acid to be considered evaluable. After the initial measurement showing a >50% decrease in PSA compared to baseline, a second measurement must confirm the decrease,

and the measurements must be at least 4 weeks apart.  $PSA_{50}$  response rate will be calculated as a proportion with 90% confidence intervals.

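### The PSA50 confirmation rule sets a strict 28-day minimum on a 28-day PSA schedule with visit windows and no tolerance, so two compliant consecutive values can fail to confirm a response

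*Combined protocol and SAP*

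**What the plan says.** Section 13.2 defines the primary endpoint as a PSA fall of 50% from baseline and adds: "The decrease must be confirmed by a second measurement at least 4 weeks apart. PSA values will be measured monthly during the trial". Section 13.7 repeats that "a second measurement must confirm the decrease" and that "the measurements must be at least 4 weeks apart". Neither section gives a tolerance, and neither requires the confirming value to be the next one drawn.

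The draw dates are set elsewhere:

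- The Study Calendar (7.1) gives a 28-day cycle and a visit window of 3 days either way. Section 7.3 repeats that window for the Day 1 visit of each cycle.
- A calendar footnote restricts PSA to Day 1: "After C1D1, PSA is collected at CnD1 only (i.e., not weekly".
- The same footnote adds a window for the draw itself: "Safety labs and PSA may be collected within a window of up to 3 days prior to scheduled visit/dosing".

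Section 13.5 assesses twelve patients for 6 months and takes the combination forward if 2 or more have a PSA50 response. It states a null rate of 3%, a target rate of 23%, alpha of 0.05 and 80% power.

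**The concern.** The shortest gap that can confirm a response equals the nominal gap between draws. Any movement of the second draw towards the first takes the pair below 28 days, even when both draws follow the schedule. A patient with two compliant consecutive values, both showing the required fall, can then remain unconfirmed unless a further qualifying value arrives.

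The rule can only remove responders, so the error goes one way. With a threshold of 2 in 12, removing one responder changes the conclusion whenever exactly two would otherwise be counted. With no tolerance written down, someone would also have to decide after seeing the data whether a 27-day confirmation counts, in a single-arm trial where one patient can settle the result.

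**Working it through.** **1. The plan's own design.** Inputs from 13.5: n = 12, go if X ≥ 2, null 3%, target 23%. With X binomial, P(X ≥ 2) = 1 − (1−p)^12 − 12p(1−p)^11.

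- p = 0.03 gives 0.0486, within the stated 0.05.
- p = 0.23 gives 0.8009, matching the stated 80%.

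The design reproduces. It has little room: power is 0.1 points above target and alpha 0.14 points below its limit. At 23%, the chance of exactly two responders is 66 × 0.23² × 0.77^10 ≈ 0.26, and in that case one unconfirmed responder reverses the decision.

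**2. Possible gaps between consecutive draws.**

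- Visit window only, each visit measured against a fixed 28-day grid: 28 ± 6, or 22 to 34 days. Failing gaps are 22 to 27 days.
- Adding the early PSA window: each draw lies between 6 days early and 3 days late, so the gap is 28 ± 9, or 19 to 37 days. Failing gaps are 19 to 27 days.
- If the visit window is instead counted from the previous visit, that window alone gives 25 to 31 days.

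**3. Share of consecutive pairs under 28 days.** If both draws have the same independent distribution of day offsets, p_d, then by symmetry P(gap < 28) = (1 − Σp_d²)/2. The documents give no distribution of draw days, so every row rests on an assumption.

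| Assumed draw days | Σp_d² | Share under 28 days |
|---|---|---|
| Uniform over ±3 days | 1/7 | 21/49 = 42.9% |
| Uniform, PSA window only (0 to 3 days early) | 1/4 | 37.5% |
| Uniform in both windows | 92/784 | 44.1% |
| 50% on the exact day, rest uniform over ±3 | 0.292 | 35% |
| 70% on the exact day | 0.505 | 25% |
| 90% on the exact day | 0.812 | 9% |
| 100% on the exact day | 1 | 0% |

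Counting the visit window from the previous visit, with uniform days, also gives 3/7 = 42.9%.

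**4. Who can lose a response.** Values two visits apart are at least 56 − 6 = 50 days apart, or 56 − 9 = 47 with both windows. A response that holds for three monthly values can therefore always be confirmed. Only a response seen on exactly two consecutive values is exposed. That happens when treatment stops soon after the fall, or when the fall first appears near month 6. Six months hold about six post-baseline monthly values, and a first fall at the fifth has only the sixth left to confirm it.

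**5. Effect on power.** Let f be the share of responders with exactly two qualifying values, and c the share of short pairs from step 3. The rate counted is 0.23 × (1 − f × c). The documents do not give f.

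| f (assumed) | Rate, c = 3/7 | Power, c = 3/7 | Power, c = 0.2475 (70% on the exact day) |
|---|---|---|---|
| 0 | 0.2300 | 80.1% | 80.1% |
| 0.05 | 0.2251 | 79.0% | 79.4% |
| 0.10 | 0.2201 | 77.8% | 78.8% |
| 0.25 | 0.2054 | 74.0% | 76.7% |
| 0.50 | 0.1807 | 66.6% | 73.0% |

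The same loss applied to the 3% null lowers exact alpha below 0.0486, so the strict rule does not inflate false positives.

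**The case against.** A reader might infer that about 43% of consecutive pairs, or of responses, will fail. The documents do not support that. The 43% needs every day in the window to be equally likely at both visits, and clinics that mostly keep to the exact day would see far less.

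Nor does a short pair by itself lose the response. The plan asks for a second measurement, not the next one, so any later qualifying PSA will do. The calendar also collects PSA at end of treatment and in long-term follow-up, and nothing in 13.2 or 13.7 excludes those values. This part of the objection stands, and it confines the problem to responders with exactly two qualifying values.

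A reader might also infer that the stated 80% power is wrong. It is not: the calculation reproduces. Section 13.5 sets 23% for PSA50 response, which 13.2 defines as confirmed. If 23% already allows for failed confirmations, power is unaffected. The reductions apply only if 23% is the rate before this loss.

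The mismatch itself survives. No passage says how to treat a compliant pair less than 28 days apart, and the end-of-treatment PSA is not a sure rescue. That visit falls within 28 days of the last dose (7.4.2), so its PSA can also come less than 28 days after the previous draw.

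**Conclusion.** The confirmation rule and the PSA schedule do not fit together. Compliant consecutive values can be 22 to 27 days apart (19 to 27 with both windows) and fail the primary endpoint rule. The share that does so is unknown; the scenarios tried run from 0% to about 44%.

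The harm is limited to responders with exactly two qualifying values. Its cost in power depends on three things that the documents leave open: how draw days spread, what share of responders is of that kind, and whether 23% is a rate before or after this loss. With uniform draw days and 23% taken before the loss, power is 77.8%, 74.0% or 66.6% for shares of 10%, 25% or 50%. This is a range under assumption, not a finding that the trial is underpowered. The point still merits a change, because the bias has one direction and the decision can turn on a single patient.

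**What to change.** In 13.2 and 13.7, replace the strict 28-day minimum with a statement that the fall is confirmed by the PSA from any later scheduled Day 1 visit, drawn within its permitted window. State there also whether an end-of-treatment PSA may confirm, since the current wording does not exclude one.

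Two tempting alternatives are weaker. A 25-day minimum overlooks that both draws can move: with uniform offsets over the visit window, 6/49 = 12% of pairs would still fail. Requiring the next scheduled PSA would remove the later confirmation that the plan now allows.

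The cost is protocol wording only. The downside is that a confirming value may come a few days under 4 weeks, which could slightly raise the rate of confirmed responses under the null. With exact alpha at 0.0486 against 0.05, this should be acknowledged when the change is made.

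Related passages need reconciling with the visit window and with each other. PSA doubling appears in 7.4, 7.4.1, 13.3 and 13.8, with a 4-week confirmation in each but the 12-week minimum missing from 13.3. PSA PFS has no interval in 13.3 and a 4-week interval between consecutive increases in 13.8. Because PSA doubling also governs the end of treatment, those passages are only flagged here, and no stopping rule is proposed.
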